
The ethical principles of which the MST Supervisor, MST Therapists and Outcomes Assessor must be aware when speaking to the young person and his or her carer about participation in the study are:

There is no negative consequence for those who decline to participate;

There is no negative consequence for those who do participate;

Potential participants are informed of all that is expected of them, including benefits and risks that may be associated with participation;

Consent to participate is freely and voluntarily given, with full appreciation of the above; Participants understand that they can withdraw their consent to continued participation at any point in the process;

All information gathered about them will remain confidential; and

Anonymity is assured in that individual participants will not be identified in any report or document produced.

Second, the MST Supervisor, MST Therapists and Outcomes Assessor understand that, for the MST clinical trial, the implications of these standards are that potential participants must understand:

What MST entails, including the amount of time spent in the home, the intensity and duration of intervention and what is expected of the participants;

That young people who decline to participate in the clinical trial will receive the same level of intervention they would normally expect from the YOS (i.e. they will not be penalised for declining consent);

That half those who sign the consent forms will receive whatever intervention would have been available to them if no MST study had been underway;

That the decision about who gets MST is made randomly so each person has an equal chance of being selected;

That the services offered to the control group are not a placebo or are not inferior but rather constitute the typical services available to young offenders as MAU;

That participation in the clinical trial entails filling out questionnaires to gather background information and after discharge from treatment or approximately five months if not allocated to MST;

That the young person's school will be approached for information;

That the parent or carer and the young person are free to drop out of the MST condition;

That all information participants provide will remain confidential except in three circumstances: 1) A person under 16 is at risk as defined in the Children Act 1989

2) a person voices a fixed intention to harm a specific other person that must be communicated to the police; or 3)the information is demanded by the judge; and

That at six-month, one-year, two-year and three-year intervals the law-breaking behavior of the young person will be checked and that this information will not be revealed to anyone outside the research group.

The verbal explanation of the study given by the MST Supervisor, MST Therapists and Outcomes Assessor to the young person and her/his parent or carer is a crucial part of the process whereby they are able to give valid consent to take part in the study. In seeking consent, the MST Supervisor, MST Therapists and Outcomes Assessor ensure the decision is made on an informed basis. Due to the vulnerability of the young person and her/his parent or principal carer, there are a number of potential misunderstandings that could lead to their giving consent on an uninformed basis and to which the MST Supervisor, MST Therapists and Outcomes Assessor must be alert, namely:

1. The young person and her/his parent or carer may think they are obliged to take part because the study is part of the young person's sentence, i.e. they may not understand the voluntary nature of the study.

2. They may think that refusal to participate will have further negative consequences for the young person.

3. They may think that if they drop out of the study that this will have negative consequences for the young person, for instance that the young person will be breached and taken back to court.

4. They may think that agreement to participate means that they automatically get MST.

5. They may not understand that the MST intervention involves the participation of the parent or carer as well as the young person.

6. The young person and his/her parent or carer may not realise the young person's decision as to whether to participate carries the same weight as the parent or principal carer and that, if the young person refuses to give consent, participation cannot go ahead even if the parent or carer agree to give their consent.

7. The capacity of the young person to understand the nature of the study will vary accoriding to her/his age. For example, a young person aged 13 years is unlikely to understand or grasp the nature of the study in the same way as a young person aged 16 years.

To guard against these and other pitfalls MST Supervisor, MST Therapists and Outcomes Assessor considers the following action points:

1. Those who have agreed to discuss the study having received the MST information leaflets may sign the consent form at the first meeting with the MST Supervisor, MST Therapists and Outcomes Assessor. Some potential participants may express an interest in the study but prefer to have time to think over their participation.

2. At the meetings, the pitfalls described above should be addressed as part of the explanation of the study given to the young person and her/his parent or carer.

3. Before the consent forms are signed, the MST Supervisor goes through the information sheet and the consent forms with the parent or carer to ensure she/he understands the study. The MST Therapist, who like the MST Supervisor is trained to work with young people, goes through the information sheet with the young person. the MST therapist interprets the information sheet to ensure that the young person understands what is involved: that her/his participation is entirely voluntary; that she/he can withdraw from the study at any time without being penalised; that at any time she/he can refuse to have her/his criminal record accessed; that should she/he get MST, this intervention is independent of services offered by the YOS; that we may offer to help in a number of areas, including education, social activities, substance abuse and anger management if these are problems that contribute to her/him getting into trouble but that he/she can refuse help in one area without jeopardising help in other areas.

Finally, the MST supervisor and therapists follow the following guidelines regarding withdrawal from the study by the young person and her/his parent or carer:

1. The decision of the young person and her/his parent or carer to withdraw from the clinical trial should at all times be respected.

2. If the young person and her/his parent or carer consistently refuse to carry out recommendations of the MST therapist, this should be interpreted as them not wanting to continue with the project.

 If the young person and her/his parent or carer consistently refuse to make appointments with the MST Therapist, this should be interpreted as not wanting to continue with the project.
 Withdrawal from the study is a barrier to future participation.

5. The data from the participants who withdraw consent should be kept until the end of the study. Once the study is over their data must be removed.

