In the event that there is no multi-agency panel and the treatment team is asked to decide if the case is acceptable, a guideline for inclusion analogous to the considerations above could be used depending on the nature of the referral. This would of course create the need for even more complex negotiations with multiple groups but we anticipate that at the end of those discussions the inclusion criteria for the four agencies might include the following:

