(1) Recruitment via Children's services: Looked after children can be looked after on a voluntary basis (section 20) or under a legal framework following court proceedings. The process for the latter is currently changing with introduction of the Public Law Outline which requires the LA to have undertaken a pre-specified set of tasks before care will be considered by the court. It also 'gives notice' to the families that care is being considered and that they need to comply with required assessments or interventions if they wish the child to remain in the family. We therefore propose that the MST RCT would be most appropriate for children designated as 'Children In Need' and who have an allocated social worker. The inclusion criteria would be broadly as above and would include additional criteria (3&4): (1) Young person aged 11-17 years; (2) sufficient family involvement for MST to be applied, excluding adolescents already in local authority care or foster accommodation, (3) no existing agency involvement (e.g. the family is already engaged with a therapist) which would interfere with MST; (4) Adolescent designated as 'Child in Need' where this is associated with antisocial behaviour on the part of the adolescent; (5) Exhibiting extremely challenging behaviour by EITHER Persistent (weekly) and enduring (6 months or longer) violent and aggressive interpersonal behaviour AND/OR a significant risk of harm to self or to others e.g. self harming, substance misuse, sexual exploitation, absconding; Recruitment via Forensic services: Those recruited via forensic services will have forensic histories indicating both severity and chronicity. Thus the inclusion criteria, in addition to the generic criteria 1, 2 and 3 above, would comprise (1) at least one conviction within the last twelve months, or referral via a supervision order with MST as specified activity, (2) a warning, reprimand and/or conviction on at least three occasions in the 18 months. Recruitment via Child Mental Health services could have the following specific criteria: (1) current

Recruitment via Child Mental Health services could have the following specific criteria: (1) current diagnosis of conduct disorder, substance misuse, major depression or anxiety; (2) history of at least one unsuccessful outpatient intervention; (3) EITHER history of school exclusion OR assessment as child in need.

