situation would change, not wishing anybody to work in the family home or planning to move out of the borough soon. 88% of those consenting and undertaking baseline assessment will be expected to participate in the trial with 12% excluded because they did not meet criteria. Thus we assume no more than about a third of those referred will participate but that 55% of appropriate referrals meeting criteria will participate with approximately 40% of those referred being excluded as failing to meet criteria. It should be noted that although these assumptions mean that only a relatively small number of those referred will be included in the trial, data indicates that immediate dropout from treatment for severe conduct problems is in any case very high (Kazdin & Wasser, 2000). Thus, those receiving MST are likely to be a much higher proportion of those adolescents who, in the real world would be willing to engage with therapeutic services for treatment. To recruit 700 adolescents who are considered at severe risk of out of home placement we would expect approximately 2,117 to be referred to the MST multi-agency panel. This means about 200-225 families referred to each site over the study period. It should be remembered that these may be conservative assumptions that reflect the severe forensic problems that characterise the BCT sample.

**Randomistion:** Eligible consenting participants will be randomised on a 1:1 basis by the Clinical Trials Unit at UCL using a secure, automated 24 hour telephone randomisation service that will ensure allocation concealment. A computer-generated adaptive minimisation algorithm that incorporates a random element will be used with the following stratification factors: treatment centre, gender, age (11-14, 15-17), age at onset of severe conduct problems (2-11, 11+), number of past convictions ( $\leq 2/\geq 3$ ). These strata have been selected because previous research (see Background) has shown that younger age of onset and greater number of previous convictions are associated with poorer prognosis and there is insufficient evidence concerning gender mix, particularly in the older age groups, to ensure that simple randomisation would generate comparable groups. Minimisation should ensure that there will be an even distribution of adolescents across the two arms of the trial.

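### The fallback forensic criteria accept referral under a supervision order that names MST, which does not fit 1:1 allocation, the bar on MST staff seeing MAU cases, or what families are told at consent

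*Protocol*

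**What the plan says.** All references are to the protocol, Design and Methodology (Randomisation to 18 month follow up).

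- **Target population, forensic services.** The first criterion is "at least one conviction within the last twelve months, or referral via a supervision order with MST as specified activity". The second, which must also be met, is "a warning, reprimand and/or conviction on at least three occasions in the 18 months". The generic criteria on age, family involvement and agency involvement apply as well.
- **Status of that list.** It is offered for the case where no multi-agency panel exists, in tentative words: "we anticipate that at the end of those discussions the inclusion criteria for the four agencies might include the following".
- **General (panel) criteria.** The offending item, (4)(c), asks for at least one conviction and three warnings, reprimands or convictions within 18 months. It has no supervision-order alternative.
- **Randomisation.** "Eligible consenting participants will be randomised on a 1:1 basis". No exception is made for ordered cases.
- **Planned intervention.** MST therapists and supervisors must not see participants in the MAU arm.
- **Methods of recruitment and consent.** Families are to understand "That the decision about who gets MST is made randomly so each person has an equal chance of being selected" and "That half those who sign the consent forms will receive whatever intervention would have been available to them if no MST study had been underway". The young person is told that "should she/he get MST, this intervention is independent of services offered by the YOS". Staff are to correct the belief that the family is "obliged to take part because the study is part of the young person's sentence", and the fear that dropping out could lead to breach and a return to court.

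**The concern.** A supervision order that names MST fixes, at least on its face, what the young person is to receive. Random allocation presupposes that either arm can be delivered. If this entrant is allocated to MAU, the text leaves two courses. Either the named activity is not provided, or MST staff see an MAU participant against the protocol's own bar. Nothing in the document chooses between them or says what becomes of the order.

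Two things are at stake. The first is consent: several scripted assurances do not fit someone whose order names MST. The second is the comparison. MST delivered in the MAU arm would shrink the placement difference. An order left undelivered would be a circumstance peculiar to MAU, and custody is one component of the primary outcome.

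**Working it through.** **1. The texts side by side, for a young person whose order names MST**

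| Protocol statement | Fit with this entrant |
|---|---|
| 1:1 allocation of all eligible consenting cases | Allocation to MAU is possible; no exception is made |
| MST staff must not see MAU participants | If kept, the named activity is not delivered; if the activity is delivered, the bar is broken |
| Equal chance of MST | True of the allocation, but at odds with an order that already names MST |
| MAU is what would have been available without the study | Hard to apply when the order itself names MST |
| MST is independent of the youth offending service | Hard to reconcile with MST named in a supervision order |
| Study as part of sentence, and breach on dropping out, are misunderstandings | The study is still not the sentence, but MST is named in the order, so the reassurance about leaving MST is no longer safe |
| General criterion (4)(c) | No supervision-order alternative, so the two lists differ |

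Neither the general criteria nor the exclusion list bars a young person under such an order. One who qualifies at a panel site on another ground would meet the same gap.

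**2. The stated power**

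Inputs from Procedure and Sample size: 350 per arm; 30% placement in MAU against 20% in MST; design effect 1.22 in the MST arm and 1 in the other; stated power 86% without clustering and 83% with it. The significance level is not given there; I assume two-sided 5%.

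Formula: power = Φ[(d − 1.96·SE0)/SE1], where d = p1 − p2, SE0 = √[p̄(1 − p̄)(1/n1 + 1/n2)], SE1 = √[p1(1 − p1)/n1 + p2(1 − p2)/n2], and p̄ is the mean risk weighted by n1 and n2.

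- No clustering: n1 = n2 = 350, p̄ = 0.25, SE0 = 0.03273, SE1 = 0.03251. Then (0.10 − 1.96 × 0.03273)/0.03251 = 1.10, and power = 86.5% (stated 86%).
- With clustering: n2 = 350/1.22 = 286.9, p̄ = 0.255, SE0 = 0.03471, SE1 = 0.03403. Then (0.10 − 1.96 × 0.03471)/0.03403 = 0.94, and power = 82.6% (stated 83%).

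Both stated figures reproduce.

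**3. Illustration of dilution**

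The protocol gives no share of entrants under such orders. Let c be the share of the MAU arm that receives MST and has the MST placement risk. The MAU risk becomes 0.30 − 0.10c and the difference 10(1 − c) points.

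| c (assumed) | MAU cases (350c) | Difference, points | Power, no clustering | Power, design effect 1.22 |
|---|---|---|---|---|
| 0 | 0 | 10.0 | 86.5% | 82.6% |
| 2% | 7 | 9.8 | 85.2% | 81.2% |
| 5% | 17.5 | 9.5 | 83.1% | 78.9% |
| 10% | 35 | 9.0 | 79.2% | 74.6% |

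Against the clustered base, the losses are about 1, 4 and 8 points.

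**The case against.** The other side has real force.

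- **The criterion is tentative.** It belongs to a fallback guideline for sites without a panel. The recruitment section assumes a panel at each site and describes a uniform recruitment protocol still under discussion. The requirement of three disposals narrows the group further. This stands, and it lowers the priority. It does not remove the conflict: the target-population section also presents its source-specific criteria as defined, only hopes for a panel at most sites, and the recruitment section provides for sites without one.
- **Consent is required to be voluntary.** A reader might infer that these young people enter without voluntary consent. The protocol does not support that. Consent must be freely given and in writing from both the young person and a parent or carer, the young person's refusal is decisive, and fears about sentence and breach are to be addressed. An order naming MST is not an order to join a trial. What stands is that voluntariness is in doubt and the scripted reassurances need care.
- **Crossover is barred by the text.** A reader might infer that each such case in MAU will cross over to MST or be breached. Neither is stated. The bar on MST staff seeing MAU cases points against crossover, and the document does not say how a specified activity binds or whether non-delivery by a service counts against the young person. These remain possibilities, with opposite effects on the estimate.
- **Dilution is a normal part of a pragmatic intention-to-treat comparison.** True, but this source of it is written into an entry criterion and can be avoided. Intention to treat keeps the groups as randomised; it does not prevent the dilution.

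**Conclusion.** The supervision-order alternative is inconsistent with the allocation rule, the bar on MST staff, several consent statements and the general offending criterion, and the protocol has no rule for the order when allocation is to MAU. That much rests on the text alone and applies from the first such referral.

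The effect on the trial result cannot be sized from the document. The figures of about 81%, 79% and 75% assume shares of 2%, 5% and 10%, delivery of MST to all of them despite the bar, full MST effect, and a two-sided 5% test. If few or none enter this way, the loss is negligible. The opposite effect, an undelivered order in MAU only that leads to custody and so favours MST, is an inference without a figure. The case for acting therefore rests on the eligibility and consent conflict more than on lost power. It is a minor to moderate point and would not by itself call the trial into question.

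**What to change.** Reconcile the forensic criteria with the general criteria, the randomisation rule, the bar on MST staff and the consent statements. The simplest way is to delete the words after the comma in "at least one conviction within the last twelve months, or referral via a supervision order with MST as specified activity". The forensic route would then, like general criterion (4)(c), rest on convictions and other disposals alone. The two lists would still differ in the look-back for the conviction (twelve months in the forensic list, 18 months in the general one), which can be aligned in the same edit.

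Because the general criteria and exclusions are also silent, add an item on the standard referral form, which already serves as the first screen, asking whether a court order names MST, so that such cases are identified before randomisation.

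The cost is one line of amendment and one tick-box. The downside is the loss of what may be a few referrals.
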